#### **D.7.b. Incidence of ADRD for the pragmatic cluster-randomized comparative effectiveness clinical trials:**

For the two pragmatic trials and using similar approach from previous studies, we will use data captured by the EHR to assess for two outcomes. The primary outcome measure will be any new ADRD case identified (documented in the EHR) within 12 months of the Annual Wellness Visit (index visit). The secondary outcome measures will be any services related to cognitive diagnostic assessment in the post Annual Wellness Visit (index) period that providers may order to diagnose or exclude ADRD. Specifically, the metrics

of diagnostic assessment will be evaluated as proportions of patients with a record of 1 or more of:

- Laboratory tests for TSH, serum B12, folate, or syphilis; individually or combined at any point during the 90 days after index
- Neuropsychological testing, including testing by psychologist or physician, technician administrator, computer, or other providers during the 12 months after index date
- Brain imaging testing (computed tomography, magnetic resonance imaging, positron emission tomography, magnetic resonance angiogram) of the head and neck, brain, or skull during the 12 months after index date
- Medications approved for management of ADRD (cholinesterase inhibitors, memantine) during the 12 months after index date

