In response to the RFA-AG-20-051 call for the "validation, and translation of screening and assessment tools for measuring cognitive decline," our interdisciplinary scientific team is proposing to execute a clinical validation study, one pragmatic trial and one additional replicated pragmatic trial among patients from diverse rural, suburban and urban primary care practices in two independent sites located in central Indiana and south Florida. As required by the RFA, the first study will be a single-arm clinical validation (NIH Stage III) study of our developed early ADRD detection approaches; Passive Digital Marker (PDM) and the Patient Reported Outcome (PRO) tool, the Quick Dementia Rating System (QDRS) for discriminating gold standard ADRD diagnoses for a sample of 400 older primary care patients served in the two states. The other studies will be two pragmatic cluster-randomized controlled comparative effectiveness (NIH Stage IV) trials to incorporate the PDM and the QDRS within the Medicare paid Annual Wellness Visit (AWV) for a cohort of patients from practices across the two independent sites, with practices randomized in each pragmatic trial to one of the 3 arms (the AWV alone, the AWV with PDM, and the AWV with both the PDM and the QDRS).

These studies will support the following aims:

**Primary Aim 1:** Evaluate the predictive performance of the PDM, the QDRS, and the combined (PDM + QDRS) approach in the early detection of ADRD, compared to the gold standard diagnoses.

*Primary Hypothesis 1:* The Area Under the Curve (AUC) for the combined approach (PDM + QRDS) will be 0.85 or greater and the AUC for the PDM or the QDRS will be 0.75 or greater.

*Secondary Hypothesis 2:* The combined approach (PDM + QDRS) will have statistically better AUC than each individual approach alone.

**Primary Aim 2:** Evaluate the practical utility and effect of the PDM, the QDRS, and the combined approach (PDM + QDRS) in improving the annual rate of new documented ADRD diagnosis in primary care practices.

*Primary Hypothesis 1:* In comparison to the AWV alone, the combined approach (PDM + QDRS) within the AWV will increase the incidence rate of ADRD over the subsequent 12 months from 6% to 13%.

*Secondary Hypothesis 2:* In comparison to the AWV alone, the combined approach (PDM + QDRS) within the AWV will have higher acceptance rates for recommended ADRD diagnostic work-up following a positive screen from 44% to 66%.

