## D. RESEARCH APPROACH

**D.1. General Overview and Design (see figure):** Our research design is predicated on the notion that patient screening would appropriately identify a more targeted group for referral for appropriate diagnostic services. We will conduct three complementary studies to evaluate the effectiveness of the PDM, the QDRS or the combined (PDM + QDRS) approaches for early detection of ADRD. These approaches will be embedded within the EHR systems of diverse rural, suburban, and urban primary care practices in central Indiana and south Florida. The first study will be a clinical validation study (stage III) of the three approaches; the PDM, the QDRS, and the combination of both (the PDM + QDRS). The approaches will be clinically validated in real-world and diverse clinical settings in comparison to the gold standard of ADRD diagnosis used in the NIA-funded ADRD Research Centers across the nation. The gold-standard evaluations will allow us to determine the accuracy of the screening approaches and compare their performances. The other studies will be two independent pragmatic cluster-randomized controlled comparative effectiveness trials (phase IV) of the approaches embedded within the AWV (PDM within AWV, PDM + QDRS within the AWV) in comparison to the current AWV only process (AWV without PDM or QDRS). The two trials will be conducted in two separate healthcare systems; the first trial will be conducted at Eskenazi Health and within 12 months a second replicated trial will be conducted at University of Miami Health. Both trials will have identical methodology and would compare the performance of the three approaches in increasing the incidence rate of new ADRD subsequently documented in the EHR by the primary care practices.

**D.2. Clinical Setting for both the Clinical Validation Study and the Pragmatic Cluster-Randomized Controlled Comparative Effectiveness Trials:** All studies will be conducted in diverse rural, suburban, and urban primary care practices in central Indiana and south Florida. Such primary care practices include 10 federally qualified health centers affiliated with Eskenazi Health in Indianapolis and 10 primary care practices in South Florida affiliated with University of Miami (UHealth). Eskenazi Health is one of the largest safety net integrated healthcare systems in the nation serving underprivileged older residents of Marion County including African Americans (50%) and dual eligible Medicaid and Medicare

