**D.4. Primary Care Practices Recruitment into the Pragmatic (Phase IV) Trials:** We will approach the practice manager and the physician leader of each primary care practice to randomize their site into one of three early detection approaches; AWV and any other visit to the primary care physician or geriatrician without PDM or QDRS; AWV and any other visit to the primary care physician or geriatrician with PDM; and AWV and any other visit with the primary care physician or geriatrician with both PDM and QDRS. We have received approval from the leadership of both Eskenazi Health and UHealth. The PDM and the QDRS will be embedded within the AWV process for each practice. The current rate of using the AWV across the country is increasing from 14% in 2012 to more than 60% in our own practices. We will obtain a waiver of informed consent from the local Institutional Review Board to review retrospectively (after at least one year of screening) the EHR systems of each practice to calculate the annual rate of new ADRD diagnosis and other EHR data to measure processes of diagnostic assessment following the AWV including screening rate, referral rate for diagnostic assessments for early ADRD and patient acceptance rate of undergoing such assessments. In addition, we will interview the practice managers by implementing a one-time completion of Practice Transformation Assessment (PTA) for each clinic enrolled in the pragmatic trial at Eskenazi Health and University of Miami Health. This will be administered by the RA or Project Manager and completed by the Practice Manager. It will be variable, we will integrate it into our research method to describe the context of our healthcare system participating in our research. We want to know if there is any difference in the results between University of Miami Health (UMiami) and Eskenazi Health, and if that is related to different practice variable specifically the payment and healthcare transformation.

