**D.5. Interventions and Control for the Pragmatic (Phase IV) Trials:** Our interdisciplinary scientific teams developed and tested both the PDM and the QDRS. Drs. [name] and [name] leveraged the widely available EHR data and the advantage of ML to develop the PDM with an approximate 80% accuracy for one-year and three-year prediction horizons. [name] team developed and tested the QDRS as a practical 2-3 minute patient reported outcome (PRO) tool for both early detection and staging of ADRD. Each pragmatic trial will randomize primary care practices into one of three approaches for early detection of ADRD at (1:1:1) ratio. These approaches include the current state of using AWV in primary care (the control group), the incorporation of the PDM into the AWV, and the combination of PDM and QDRS (Passive + QDRS). All of the three approaches will be implemented within the current Medicare funded AWV and will be integrated within the provider clinical encounter to accommodate the clinical flow and data capture and results display needs of the primary care practices. To randomly assign each practice to one of the three screening approaches, we will use a computer-generated randomization scheme.

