Potential problems & alternative strategies: The distributional assumptions for the binary outcomes are minimal, which will decrease the need to consider alternative analytic methods and models. However, to ensure the analytic methods appropriately account for the clustering effect when estimating standard errors and p-values, we will perform bootstrap estimation (i.e., using 1,000 datasets resampled with replacement at the person level) of the standard errors and confidence intervals surrounding the estimated values for AUC and % accuracy, and the estimated values for the difference in these values between screening approaches. In addition, if missing data occur, we will impute data using the simulation-based “Multiple Imputation” method, in which multiple complete datasets with plausible values for missing data are generated using model-based prediction, and analytic results from imputed datasets are aggregated to calculate appropriate standard errors and p-values in the presence of imputed data. We will use 100 imputed datasets, even though 10 to 50 are considered sufficient. Inclusion of potential auxiliary variables in the imputation model will be considered. A sensitivity analysis will be performed using participants with complete data.

**D.8.b. Primary Aim 2:** Evaluate the practical utility and effect of the PDM, and the combined methods in improving the annual rate of new documented ADRD diagnosis in primary care practices.

For Primary Hypothesis 1, three pragmatic screening approaches (AWV alone, AWV + PDM, and AWV + PDM + QDRS) will be compared on the annual incidence rate of EHR documented ADRD using nonlinear mixed models to account for clinic-clustered data. In the two pragmatic trials, different patients are randomized (via their clinics) to each of the 3 arms, making the outcomes independent between the three screening approaches; however, data will still be correlated for Aim 2 due to clustering of patients within clinics, which will be handled by random effects in the mixed models. We hypothesize the incidence rate will be 6% using AWV alone and 13% with the screening approach that combines AWV + PDM + QDRS. Incidence rates for all arms, including for AWV + PDM, will be calculated along with their 95% confidence interval.

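### Section D.4 lets the screening tools run at any visit while the primary outcome clock starts at the Annual Wellness Visit; the tool visit and the index visit must be reconciled

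*Combined protocol and SAP*

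**What the plan says.** The primary outcome in D.7.b is "any new ADRD case identified (documented in the EHR) within 12 months of the Annual Wellness Visit (index visit". The Specific Aims confirm that the window runs forward: the combined approach "within the AWV will increase the incidence rate of ADRD over the subsequent 12 months from 6% to 13" per cent. D.7.b times the secondary diagnostic-process outcomes from the same index.

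The sections differ on where the tools, the Passive Digital Marker (PDM) and the Quick Dementia Rating Scale (QDRS), are used.

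- **D.4, arm definitions.** The combined arm is "AWV and any other visit with the primary care physician or geriatrician with both PDM and QDRS" and the control arm is "AWV and any other visit to the primary care physician or geriatrician without PDM or QDRS". The PDM arm is worded in parallel.
- **D.4, two sentences later.** "The PDM and the QDRS will be embedded within the AWV process for each practice".
- **D.5.** "All of the three approaches will be implemented within the current Medicare funded AWV".
- **D.1.** The trials are "of the approaches embedded within the AWV (PDM within AWV, PDM + QDRS within the AWV".
- **D.8.b.** The analysis compares "three pragmatic screening approaches (AWV alone, AWV + PDM, and AWV + PDM + QDRS".
- **D.6.** The decision-support engine starts when a patient registers at the clinic; the type of visit is not named.

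C.3 and D.9 also describe the tools as integrated in the AWV. The Data and Safety Monitoring Plan (opening text, review-frequency table, and Event Detection and Reporting) speaks of AWV use with and without the tools and of positive screens at the AWV.

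**The concern.** Under the D.4 arm definitions, a patient in a tool practice can be screened at an ordinary visit months before an AWV. The intervention has then begun, but the outcome clock has not. A diagnosis prompted by that screen and recorded before the AWV would precede time zero. A flag could also change whether the patient attends an AWV, and so whether the patient enters the AWV-indexed population at all.

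Control practices see patients at the same kinds of visit but have no tool that could cause either effect. Any resulting loss or selection of cases would therefore differ by arm, and randomising practices does not remove it, because it happens after randomisation. What is at stake is the primary contrast of Aim 2, 6% against 13%.

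**Working it through.** No arithmetic settles this point. The check is to read the sections together and follow patients through each reading.

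**Step 1. What the text supports.** The any-visit reading rests on one sentence of D.4, although its phrase appears three times, once per arm. The AWV-only reading is supported by a later sentence of D.4, the Specific Aims, C.3, D.1, D.5, D.9 and the monitoring plan, and by the arm labels in D.8.b. D.6 is compatible with either. The weight of the text favours AWV-only, but nothing withdraws the arm definitions.

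**Step 2. Patient paths if the tools run at any visit and the AWV is the index.**

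1. *Screened at another visit, diagnosis recorded before the AWV.* The case precedes the window. That it would not count is an inference, from the word new in D.7.b and from the earlier AWV cohort in C.2, which required no evidence of dementia before its index date and whose approach D.7.b says it follows. Losses of this kind caused by the tools arise only in tool practices and would shrink the difference.
2. *Screened at another visit, diagnosis recorded within 12 months after the AWV.* The case counts, although the screen came before time zero.
3. *Flagged at another visit, and the flag prompts an AWV.* Attendance becomes a consequence of the arm. If it brings in more cases than non-cases, the tool arm's rate rises and the effect is overstated.
4. *Screened at another visit, never has an AWV.* There is no index date, so the patient is outside the outcome population. This affects the contrast only if attendance differs by arm.

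Paths 1 and 3 work in opposite directions.

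**Step 3. Patient paths if the tools run only at the AWV.** With the first AWV after trial start as the index, the tools cannot act on a patient before time zero, so paths 1 and 3 close. If a later AWV were the index, the first could already have prompted a diagnosis and path 1 would reopen. D.7.b does not say which AWV is the index when a patient has more than one.

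**Step 4. Can it be sized?** The planned excess is 13 − 6 = 7 percentage points. To say how much of it could fall outside the window, or how far selection could inflate it, one needs three things:

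- the share of patients screened at another visit before an AWV;
- the interval from screen to recorded diagnosis;
- the effect of a flag on AWV attendance, in cases and in non-cases.

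The documents give none of these. The AWV rate of more than 60% in D.4 has no stated period or denominator. The size therefore cannot be calculated, and any power figure would only reflect assumed inputs.

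**The case against.** The strongest reply is that this is a drafting slip. One sentence in a section on recruiting practices stands against most of the protocol, and the outcome definition agrees with the majority. That is largely right, and it is why the bias is stated only conditionally. It does not dispose of the point: the sentence defines the arms, it covers the control arm as well, and D.6 does not correct it.

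A second reply is that patients without an AWV are simply out of scope in every arm. That stands. A reader might infer that their exclusion is itself a bias, but it is one only if attendance differs by arm, and no section says that it does.

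A reader might also infer that the effect will be diluted and power lost. The documents do not support this, because a flag could instead bring cases to the AWV. Nor can that opposite effect be assumed large, since a flag also reaches non-cases: Table 3 gives the one-year combined PDM model an accuracy of 77.43%, so 100 − 77.43 = 22.57% of classifications were wrong.

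Finally, repeat AWVs should not be argued from the two years of screening mentioned in D.8.c. With 5 clusters in each of 3 arms, 15 × 175 = 2,625, so the conservative total of about 2,600 matches one year. The need to name the index AWV rests on the silence of D.7.b, not on that sentence.

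**Conclusion.** The inconsistency is real and should be corrected, because two stated rules together allow the intervention to start before time zero in tool practices only. If the tools run at any visit, the AWV-indexed primary contrast could be biased, in a direction and by an amount that the documents do not allow anyone to derive. If they run only at the AWV, which most of the text supports, and the first such AWV is the index, this bias does not arise and the text alone is at fault.

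A reader might conclude that the primary analysis is biased as planned. That goes too far: it assumes that the minority wording governs. The conclusion also rests on the inference that diagnoses recorded before the AWV are not counted as new, which D.7.b implies but does not state.

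**What to change.** Reconcile D.4, D.5 and D.6 so that the visit at which the tools fire is the visit that starts the primary outcome clock.

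**If the tools are meant for the AWV only:** correct the arm definitions in D.4 and limit the D.6 trigger to AWV registrations. In D.7.b, define the index as each patient's first AWV on or after the trial start date, and fix dementia-free status at that date. Report AWV attendance by arm. The cost is protocol and analysis-plan text, plus a check that the Epic trigger matches it.

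**Only if the sponsor intends any-visit use:** index all three arms, controls included, at the first eligible primary care visit on or after a common start date. Fix dementia-free status at that visit, include patients with no AWV, count new diagnoses for 12 months, and keep the AWV-indexed analysis as a sensitivity analysis. This needs a different index-date query but no new data collection, since D.7 already draws records from patients of all enrolled practices. The downside is substantial: the question in the Specific Aims changes from screening within the AWV to screening at any visit, and both the 6% control rate, which comes from AWV attenders (C.2), and the power must be rechecked.

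In either case, settle the index before the retrospective data retrieval described in D.4, so that time zero is not chosen with outcomes in view.

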## C. PRELIMINARY WORK

**C.1. Our interdisciplinary scientific team (see key personnel):** Under the leadership of Drs. [name], [name], and [name], we have assembled an impressive cadre of senior and junior scientists with expertise in ADRD screening and diagnosis (Drs. [name], [name], and [name]); Machine Learning ([name] and [name]); Psychometrics (Drs. [name], [name], and [name]); Medical informatics (Drs. [name], [name], and [name]); and Implementation Science ([name], [name], and [name]). The members of this team have a track record of collaborating in conducting research activities similar to the proposed activities within this application including creation and validation of PROs and utilization of ML algorithms to improve ADRD detection through the EHR. In the following section, we summarize the results of preliminary and relevant studies conducted by members of this team which informed the design of our proposed studies. Such preliminary studies are selected from a large repository of research conducted by this team (see scientific contributions within the key personnel).

**C.2. The limited impact of the current AWV on early detection of ADRD:** We conducted a retrospective matched cohort study to examine the impact of the AWV on the detection of ADRD. The cohort included 5% sample of Medicare beneficiaries continuously enrolled for 12 months before and after an index ambulatory visit with no evidence of ADRD before the index date. The matching process resulted in 66,399 matched pairs of beneficiaries with and without an AWV. Outcomes included 12 months post-index visit claims-based measurements of new ADRD diagnoses, medications for ADRD, and cognitive care-related diagnostic work up such as neuropsychological testing, brain imaging, blood tests for thyroid-stimulating hormone (TSH), serum B12, folate, or syphilis. *There were no clinically relevant differences between the AWV and control groups in the rates of incident ADRD diagnoses (6.16% versus 6.86%, p<0.001) and the initiation of ADRD medications (1.00% versus 1.08%, p=0.148).* While the AWV was correlated with an increase in some measures of cognitive care (e.g., TSH, B12, and folate testing), we did not find that the current AWV increased recognition of undetected ADRD. Enhancing the AWV with data from the PDM, the QDRS, or both may overcome current AWV shortcomings.

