For Secondary Hypothesis 2, the analyses will be the same as described for Hypothesis 1 of Aim 2, except that the outcome will be acceptance rates for recommended ADRD diagnostic work-up following positive screen. We hypothesize the acceptance rate will be 44% using AWV alone and 66% with the screening approach that combines AWV + PDM + QDRS.

Potential problems & alternative strategies: Same as those described for Aim 1 above.

**D.8.c. Sample Size & Power:** Calculations were performed with PASS, a comprehensive power and sample size software. All calculations assume two-sided tests and alpha = 0.05. For study 1 (i.e., Aim 1), a sample size of 15 cluster pairs consisting of 400 persons (26.667 persons per cluster) will provide 81% power to compare population values of 75% versus 85% in the outcome of % accuracy of classification. This is based on using nonlinear mixed models to compare two paired (i.e., dependent) proportions. The proportions are considered dependent instead of independent because all three screening approaches for study 1 will be performed in the same sample of 400. This approach was selected because it will increase power by allowing participants to serve as their own controls. Moreover, it is appropriate for a diagnostic validity study to compare methods in the same sample (i.e., method contamination is not an issue). This calculation assumes that participants are recruited from 15 clinics (i.e., clusters) and that the within-pair coefficient of variation (CV) between clusters is .058. The CV was calculated as  $CV = \text{SQRT} (ICC \times (1 - \phi) / \phi)$ , where the intraclass correlation coefficient (ICC) was assumed to be 0.01, and phi is 0.75 (i.e. the proportion of accuracy for one of the standard screening methods). The power will be slightly greater than 81% to detect values of 75% versus 85% in the AUC, based on power for comparing two dependent AUC's, assuming discrete cutoff values, and accounting for a sample inflation factor (IF), where  $IF = [1 + (M - 1) * ICC]$ , M = average number of persons per cluster, and the ICC is 0.01.

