Because the other studies are two separate pragmatic clinical trials, participants will be cluster-randomized to three different arms. This approach ensures that rigorous testing of the outcomes (incident ADRD detection and acceptance of subsequent diagnostic assessments) is not contaminated by the other screening approaches in other arms of interest. In addition, the 400 patients in study 1 will be excluded from the two pragmatic trials to avoid contamination. The total sample for each pragmatic trial will be slightly over 2,600, if each of enrolled practice screen conservatively 175 patients per year for a total of two years of screening. Alternatively, the total sample size for each trial will be 3,600, if we recruit, as we have in past trials, 200 patients per clinic. The table below shows the power for comparing ADRD incidence and acceptance rates between two different arms under the conservative and historical recruitment scenarios. Calculations were based on using nonlinear mixed models to compare two independent proportions, assuming cluster randomization (i.e., level-2 randomization) and the

ICC is 0.01. The “AWV alone” arm is expected to have ADRD incidence of 6% and acceptance rate of 44%. The table shows that power will exceed 80% to detect ADRD incidence of 6% vs 13%, even under conservative recruitment projections, and power for comparing acceptance rates will be 99%.

Outcome	Conservative recruitment* (N = 2,600)	Projected (feasible historically) recruitment* (N = 3,600)
ADRD incidence 6% vs 13%	86%	89%
Acceptance 44% vs 66%	99%	99%

\*Conservative recruitment = Total of 2,600 patients with 866 patients and 5 clusters per each of 3 arms; power for pairwise comparisons based on 1,732 patients with 866 patients and 5 clusters per each of 2 arms, and M = 173.2 patients per cluster. Historical recruitment = Total of 3,600 patients with 1,200 patients and 5 clusters per each of 3 arms; power for pairwise comparisons based on 2,400 patients with 1,200 patients and 5 clusters per each of 2 arms, and M = 240 patients per cluster.

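### The pragmatic trials' secondary outcome is recorded service use in D.7.b but acceptance of work-up after a positive screen in D.8.b, and the 99% power matches neither definition

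*Combined protocol and SAP*

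**What the plan says.** Section D.7.b announces two EHR outcomes for the pragmatic trials. The primary is a new documented ADRD case within 12 months of the index visit. For the other, it says the "secondary outcome measures will be any services related to cognitive diagnostic assessment in the post Annual Wellness Visit (index) period that providers may order", and that the metrics "of diagnostic assessment will be evaluated as proportions of patients with a record of 1 or more of" four groups of items. These are laboratory tests (90 days), neuropsychological testing (12 months), brain imaging (12 months) and "Medications approved for management of ADRD (cholinesterase inhibitors, memantine) during the 12 months after index date". No item depends on a positive screen, and acceptance is not mentioned.

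The Specific Aims state Secondary Hypothesis 2 for the combined approach against AWV alone as "higher acceptance rates for recommended ADRD diagnostic work-up following a positive screen from 44% to 66" percent. D.8.b analyses it in the same way as the primary outcome, except that "the outcome will be acceptance rates for recommended ADRD diagnostic work-up following positive screen". It gives no analysis or expected rate for the D.7.b items.

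D.4 lists, as measures to be taken from the EHR, "screening rate, referral rate for diagnostic assessments for early ADRD and patient acceptance rate of undergoing such assessments", without saying how acceptance is recognised in the record. The Data and Safety Monitoring Plan reports completion, and non-completion, of the diagnostic assessment after a positive screen, again with no link to the D.7.b items.

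D.8.c says "power for comparing acceptance rates will be 99" percent. Its table footnote bases this on 866 patients per arm (conservative) or 1,200 per arm (historical), with 5 clusters per arm.

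**The concern.** The outcome section and the analysis section describe different quantities:

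- **Event.** D.7.b counts a recorded service or drug. D.8.b counts a patient's acceptance of work-up that was recommended.
- **Denominator.** D.7.b refers to patients after an index visit. D.8.b refers to patients with a positive screen.
- **Window.** D.7.b gives 90 days or 12 months. D.8.b gives none.

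A routine thyroid test counts under D.7.b but is not by itself acceptance of recommended work-up. An ADRD prescription counts as diagnostic assessment under D.7.b, although it is treatment.

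The secondary outcome that is defined therefore has no analysis, and the one that is tested has no operational definition. The data are extracted retrospectively from the EHR, so the choice could be made after results are visible, and the same data could support the hypothesis under one definition and not under the other. The power statement adds to the problem: its rates come from one definition and its denominator from the other.

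**Working it through.** **Inputs (all D.8.c unless noted).** Two-sided alpha 0.05; ICC 0.01; 5 clusters per arm; M = 173.2 (conservative) or 240 (historical) patients per cluster; 44% v 66% (also D.8.b); 6% v 13% for the primary outcome. The screen-positive share s is not in the documents and is an assumption, taken as equal in both arms and across clinics.

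**Formulas.** Patients counted per cluster: m = s × M. Effective n per arm: n = 5m / [1 + (m − 1) × 0.01]. SE = √{[p1(1 − p1) + p2(1 − p2)] / n}. Power = Φ(|p1 − p2| / SE − 1.96).

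**Step 1: reproduce the plan, with every patient counted (s = 1).** Design effects are 1 + 172.2 × 0.01 = 2.722 and 1 + 239 × 0.01 = 3.390. Effective n is 866 / 2.722 = 318.1 and 1,200 / 3.390 = 354.0.

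- 6% v 13%: the variance sum is 0.0564 + 0.1131 = 0.1695, the SE is 0.0231 and 0.0219, and power is 86% and 89%. Both match the table.
- 44% v 66%: the variance sum is 0.2464 + 0.2244 = 0.4708, the SE is 0.0385 and 0.0365, and power is above 99.9% in both scenarios. This agrees with the stated 99%.

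The same formula reproduces both rows of the table only with all enrolled patients. The acceptance row is therefore not restricted to screen-positive patients.

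**Step 2: restrict to screen-positive patients, as D.8.b defines acceptance.** Worked case, s = 10%, conservative: m = 17.32, design effect 1.163, n = 86.6 / 1.163 = 74.4, SE = √(0.4708 / 74.4) = 0.0795, 0.22 / 0.0795 = 2.77, power = Φ(2.77 − 1.96) = 79%.

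| Assumed share positive | Conservative: positives per arm, power | Historical: positives per arm, power |
|---|---|---|
| 5% | 43, 53% | 60, 65% |
| 10% | 87, 79% | 120, 89% |
| 20% | 173, 95% | 240, 98% |
| 30% | 260, 99% | 360, >99% |

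A pooled null variance lowers these by at most about 2 points (for example 51% instead of 53%).

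**Step 3: what 99% requires.** About 276 screen-positive patients per arm with this formula, or about 286 with pooled variance. That is 32–33% of 866 or 23–24% of 1,200.

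**Step 4: sensitivity to the small number of clusters.** A t reference with 8 degrees of freedom (10 clusters minus 2) gives 68% and 89% at shares of 10% and 20% (conservative), and 79% and 95% (historical). The plan's primary-outcome figures do not reproduce with this reference (76% and 80%), so it is shown only as a sensitivity check.

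**The case against.** The best defence is that these are two sets of measures and not rival definitions of one. D.7.b uses the plural, D.4 names acceptance as an EHR measure, the monitoring plan follows completion after a positive screen, and Secondary Hypothesis 2 is worded consistently in the Specific Aims, D.8.b and D.8.c. Nothing says that the hypothesis will be tested on the D.7.b list. This reading is reasonable, and it removes any claim that the plan has committed itself to the wrong endpoint. It does not remove the gap: D.7.b says there are two outcomes and acceptance is neither of them, the service items have no analysis, and no section says what record counts as acceptance, by when, or among whom in the AWV-alone arm.

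Three stronger inferences should be resisted.

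- A reader might put a power on the D.7.b measures by assuming a screen-positive share and a background rate of qualifying records. The result would come from those assumptions and from treating the list as one any-item composite. D.7.b does not clearly say that: it speaks of proportions in the plural and of laboratory tests taken individually or combined. Counting over all index patients is also implied there, not written.
- A reader might infer from C.2, where the "AWV was correlated with an increase in some measures of cognitive care (e.g., TSH, B12, and folate testing") without better recognition of ADRD, that the laboratory item is uninformative. That was a retrospective comparison of AWV with no AWV, and it does not bear on whether D.7.b and D.8.b agree.
- A reader might take the 99% as sound for acceptance and doubtful only for service use. The footnote to the power table rules that out.

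**Conclusion.** The point holds. The secondary outcome defined in D.7.b and the endpoint tested in D.8.b differ in event, denominator and window, and neither is fully specified. The 44% and 66% belong to acceptance, while the 99% is calculated on every enrolled patient, so it matches neither definition.

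With the denominator that D.8.b implies, power runs from about 53% to 99% (conservative) or 65% to above 99% (historical) as the screen-positive share goes from 5% to 30%. It falls below 80% once the share drops under roughly 10–11% or 7–8% respectively. These figures rest on an assumed share that is equal in both arms, an ICC of 0.01 retained in the subset, and 44% v 66% holding among screen-positive patients.

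A reader might conclude that Secondary Hypothesis 2 is underpowered. The documents do not show that, because they give no screen-positive share, and at 20% or more the normal-approximation power is 95% or higher. What they show is that the stated 99% is not tied to its own endpoint. This is a secondary endpoint and should be settled before the EHR data are extracted.

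**What to change.** 1. Name acceptance as the single Secondary Hypothesis 2 endpoint, in identical words in D.7.b and D.8.b.
2. Define it as a recorded, completed, recommended work-up service within a stated window from the index visit. Say which EHR records qualify.
3. State a denominator that can be formed in every arm, including AWV alone. It cannot depend on a PDM or QDRS result that the control arm does not have.
4. Report the D.7.b service items as separate additional outcomes over index patients. Say whether each item or a composite is analysed, and list the ADRD-drug item apart from diagnostic assessment. State that 44%, 66% and 99% do not apply to them.
5. In D.8.c, replace the 99% with power recomputed on the matching denominator over a stated range of screen-positive shares.

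The cost is wording in D.7.b and D.8.b and one recalculation in D.8.c. No patients or data fields are added. The downside is a less favourable stated power for the secondary hypothesis.
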